9.0 Safety Analyses

9.1 General Considerations

All safety analyses or summaries will be performed by study intervention group using the safety population, for overall and for each age group (6 to 11 years and 12 to 18 years in FC; 7 to 11 years and 12 to 18 years in IBS-C) separately for FC and IBS-C participants.

For each safety parameter (laboratory, vital signs, body weight, height, and ECG), the baseline will be defined as below:

- If participants enroll into LIN-MD-66 within 28 days of last dose date of the lead-in study, baseline of the lead-in study will be used as the baseline value in LIN-MD-66.
- If participants enroll into LIN-MD-66 after 28 days of last dose date of the lead-in study, the last non-missing assessment made before the first dose of the study intervention in this study will be used as the baseline value in LIN-MD-66.

Safety data analyses will be provided descriptively based on the observed safety data, without data imputation for missing safety parameters.

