9.4 Analysis of Vital Signs

Descriptive statistics for vital signs (supine systolic and diastolic blood pressure, supine pulse rate, respiration rate, and temperature, and weight) and their changes from baseline at each assessment timepoint will be presented for each vital sign measurement.

Vital sign values will be considered to be PCS values if they meet both the observed-value criteria and the change-from-baseline-value criteria as defined in Table B-2 in [Appendix B](#). The number and percentage of participants who have PCS postbaseline vital sign values will be tabulated. The percentages will be calculated relative to the number of participants who have available non-PCS baseline values and at least 1 postbaseline assessment. The numerator will be the total number of participants with at least 1 PCS postbaseline value. A supportive listing of participants with PCS postbaseline values will be provided for the Safety Population.

In addition, a tabular display showing all AEs that occurred in participants who had PCS postbaseline vital sign values will be provided.

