Appendix B. Potentially Clinically Important Criteria for Safety Endpoints

The potentially clinically significant criteria for clinical laboratory parameters, vital signs and ECG parameters are provided in the following sections.

Table B-1. Criteria for Potentially Clinically Significant Laboratory Results

Parameter	SI Unit	Lower Limit	Higher Limit
Chemistry			
Albumin	g/L	< 0.9 × LLN	> 1.1 × ULN
Alanine aminotransferase (ALT)	U/L	—	≥ 3 × ULN
Alkaline phosphatase	U/L	—	≥1.2 x ULN: 6-12 (inclusive), male & female; 13-15 (inclusive), male ≥ 3 × ULN: 13-15 (inclusive), female; 16-18 (inclusive), male & female
Aspartate aminotransferase (AST)	U/L	—	≥ 3 × ULN
Bicarbonate	mmol/L	< 0.9 × LLN	> 1.1 × ULN
Bilirubin, total	μmol/L	—	> 1.5 × ULN
Calcium	mmol/L	< 0.9 × LLN	> 1.1 × ULN
Chloride	mmol/L	< 0.9 × LLN	> 1.1 × ULN
Cholesterol, Total	mmol/L	—	> 1.6 × ULN
Creatinine	μmol/L	—	> 1.3 × ULN
Glucose, random, serum	mmol/L	< 0.8 × LLN	> 1.4 × ULN
Potassium	mmol/L	< 0.9 × LLN	> 1.1 × ULN
Protein, total	g/L	< 0.9 × LLN	> 1.1 × ULN
Sodium	mmol/L	< 0.9 × LLN	> 1.1 × ULN
Magnesium	mmol/L	< 0.9 x LLN	> 1.1 x ULN
Urea Nitrogen (BUN)	mmol/L	—	> 1.2 × ULN
Hematology			
Basophils, absolute cell count	10 ⁹ /L	—	> 3 × ULN
Eosinophils absolute cell count	10 ⁹ /L	—	> 3 × ULN
Lymphocytes absolute cell count	10 ⁹ /L	< 0.7 × LLN	> 1.3 × ULN
Monocytes, absolute cell count	10 ⁹ /L	< 0.5 × LLN	> 2.0 × ULN
Neutrophils, absolute cell count	10 ⁹ /L	< 0.8 × LLN	> 1.5 × ULN

Parameter	SI Unit	Lower Limit	Higher Limit
Hematocrit	Ratio	$< 0.9 \times \text{LLN}$	$> 1.1 \times \text{ULN}$
Hemoglobin	g/L	$< 0.9 \times \text{LLN}$	$> 1.1 \times \text{ULN}$
Platelet count	$10^9/\text{L}$	$< 0.5 \times \text{LLN}$	$> 1.5 \times \text{ULN}$
Red blood cell count	$10^{12}/\text{L}$	$< 0.9 \times \text{LLN}$	$> 1.1 \times \text{ULN}$
White blood cell count	$10^9/\text{L}$	$< 0.7 \times \text{LLN}$	$> 1.5 \times \text{ULN}$
Urinalysis			
pH	—	$< 0.9 \times \text{LLN}$	$> 1.1 \times \text{ULN}$
Specific gravity	—	—	$> 1.1 \times \text{ULN}$

LLN = lower limit of normal value provided by the laboratory; SI = *Le Système International d'Unités* (International System of Units); ULN = upper limit of normal value provided by the laboratory

Table B-2. Criteria for Potentially Clinically Significant Vital Signs

Parameter	Flag	Criteria ^a	
		Observed Value	Change From Baseline

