Systolic Blood Pressure, mmHg - Postural Vital Signs (Supine and Standing)		Decrease in systolic blood pressure of 20 mmHg or more from supine to standing [*Change from supine SBP ≤ -20]	Decrease in SBP from supine to standing at observed time point is at least 10 mmHg greater than the decrease in SBP from supine to standing at baseline [Postbaseline change from supine SBP – baseline change from supine SBP ≤ -10]
Diastolic Blood Pressure, mmHg Postural Vital Signs (Supine and Standing)		Decrease in diastolic blood pressure of 10 mmHg or more from supine to standing [Change from supine DBP ≤ -10]	Decrease in DBP from supine to standing at observed time point is at least 10 mmHg greater than the decrease in DBP from supine to standing at baseline [Postbaseline change from supine DBP – baseline change from supine DBP ≤ -10]
Pulse Rate, bpm - Postural Vital Signs (Supine and Standing)		Increase in heart rate of 20 beats per minute or more from supine to standing [Change from supine pulse rate ≥ 20]	Increase in heart rate from supine to standing at observed time point is at least 10 beats per minute greater than the increase in heart rate from supine to standing at baseline [Postbaseline change from supine pulse rate – baseline change from supine pulse rate ≥ 10]

Parameter	Flag	Criteria^a	
		Observed Value	Change From Baseline
Systolic Blood Pressure, mm Hg (Supine)	High	Age 6-11 (inclusive): ≥ 140 Age 12-18 (inclusive): ≥ 155	Increase of ≥ 20
	Low	Age 6-11 (inclusive): ≤ 80 Age 12-18 (inclusive): ≤ 90	Decrease of ≥ 20
Diastolic Blood Pressure, mm Hg (Supine)	High	Age 6-11 (inclusive): ≥ 95 Age 12-18 (inclusive): ≥ 105	Increase of ≥ 15
	Low	Age 6-11 (inclusive): ≤ 40 Age 12-18 (inclusive): ≤ 45	Decrease of ≥ 15
Pulse Rate, bpm (Supine)	High	Age 6-11 (inclusive): ≥ 140 Age 12-18 (inclusive): ≥ 120	Increase of ≥ 15
	Low	Age 6-11 (inclusive): ≤ 50 Age 12-18 (inclusive): ≤ 40	Decrease of ≥ 15
Weight, kg	High	—	Increase of $\geq 5\%$
	Low	—	Decrease of $\geq 5\%$

bpm = beats per minute; DBP = diastolic blood pressure; SBP = systolic blood pressure

* Change from supine value = standing value – supine value.

a. A postbaseline value is considered potentially clinically significant if it meets both the observed-value and the change-from-baseline criteria.

Table B-3. Criteria for Potentially Clinically Significant Electrocardiograms

Parameter	Unit	Higher Limit

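### SAP 9.4 omits the postbaseline height summary that Protocol 9.4.3 requires, and the flat 5% rule in Table B-2 lets ordinary growth count as a potentially clinically significant weight gain

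*SAP*

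**What the plan says.** **Height.** Protocol 9.4.3 asks for descriptive statistics for height at baseline and for change from baseline. SAP 3.2 lists height among the safety parameters, and SAP 9.1 gives it a baseline rule: "For each safety parameter (laboratory, vital signs, body weight, height, and ECG), the baseline will be defined as below". SAP 9.4 then names the variables to be summarised: "Descriptive statistics for vital signs (supine systolic and diastolic blood pressure, supine pulse rate, respiration rate, and temperature, and weight". Weight is there and height is not. SAP 7.1 summarises height as a baseline characteristic only.

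**Weight.** In SAP Appendix B, Table B-2, the weight row has a dash under the observed value. Its High change criterion is "Increase of $\geq 5" per cent, with a matching 5% decrease for Low. Footnote a to the table states: "A postbaseline value is considered potentially clinically significant if it meets both the observed-value and the change-from-baseline criteria". SAP 9.4 and Protocol 9.4.3 contain the same two-part requirement. One flagged visit is enough to count a participant, and SAP 9.4 adds: "In addition, a tabular display showing all AEs that occurred in participants who had PCS postbaseline vital sign values will be provided".

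**Baseline.** Under SAP 9.1, for anyone enrolling within 28 days of the last lead-in dose, "baseline of the lead-in study will be used as the baseline value in LIN-MD-66". Later entrants use the last assessment before the first dose in this study.

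**The concern.** Height and weight are named safety assessments for the primary objective of a study in growing children. A programmer who follows the SAP text alone would produce no postbaseline height result.

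For weight, the same 5% applies to a 6-year-old and an 18-year-old, and to 24 weeks as to more than a year. The rest of Appendix B does allow for development: supine blood pressure and pulse, QRS and PR have age bands, and alkaline phosphatase has age and sex bands. Weight, the measure most directly tied to growth, has none. A child who is simply growing can therefore be reported as having a potentially clinically significant value, and that child's adverse events then appear in the display meant to put abnormal vital signs in context. That display also serves the postural blood pressure, postural pulse and weight-loss criteria. These bear on volume depletion, which is part of the adverse event of special interest.

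**Working it through.** **Height.** No arithmetic applies. Protocol 9.4.3 requires baseline and change. SAP 3.2 and 9.1 treat height as a safety parameter with a defined baseline. The protocol measures height at EOT for everyone (Tables 1-1 to 1-4, Sections 10.10.7 and 10.10.11). SAP 9.4 omits it, and no other SAP section gives a postbaseline height result. For rollovers, Tables 1-1 and 1-3 schedule height only at EOT, so their baseline height has to come from lead-in data, as SAP 9.1 already provides.

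**Weight: time from baseline to EOT.** The plan states no derived figure to reproduce; the 5% is a set criterion. Inputs: treatment of 24 weeks (FC) or 52 weeks (IBS-C); lead-in treatment of 4 weeks (LIN-MD-63) or 12 weeks (LIN-MD-64) from SAP 2.2; a gap of 0 to 4 weeks for rollovers from SAP 9.1. Assumption: the lead-in baseline is taken at the start of lead-in treatment, which the documents do not state.

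Steady annual gain that reaches +5% at w weeks = 1.05^(52/w) − 1.

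| Route | Weeks to EOT | Annual gain that triggers High |
|---|---|---|
| FC, entry after 28 days | 24 | 11.15% |
| FC rollover from LIN-MD-64 | 12 + (0 to 4) + 24 = 36 to 40 | 7.30% to 6.55% |
| IBS-C, entry after 28 days | 52 | 5.00% |
| IBS-C rollover from LIN-MD-63 | 4 + (0 to 4) + 52 = 56 to 60 | 4.63% to 4.32% |
| IBS-C rollover from LIN-MD-64 | 12 + (0 to 4) + 52 = 64 to 68 | 4.04% to 3.80% |

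FC and IBS-C are reported separately, so the mixing of spans is within indication: 24 with 36 to 40 weeks, and 52 with 56 to 68 weeks.

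**Who is flagged under assumed growth.** The documents give no growth rates, so this is a range and not an estimate. Weeks to +5% at steady annual growth g = 52 × ln(1.05) / ln(1 + g).

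| Assumed g | Weeks to +5% | Flagged by EOT |
|---|---|---|
| 2% | 128.1 | No route |
| 4% | 64.7 | Only LIN-MD-64 IBS-C rollovers with a gap of about 5 days or more (64.7 − 64 = 0.7 week) |
| 6% | 43.5 | Every IBS-C route, no FC route |
| 8% | 33.0 | Every IBS-C route and FC rollovers, not FC late entrants |
| 10% | 26.6 | Same as at 8% |

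At 10%, an FC rollover is first flagged at Week 16 (12 + 16 = 28 weeks from baseline with no gap). An FC late entrant growing at the same rate is not flagged by Week 24. The baseline rule alone makes the difference.

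**Illustration only.** A 5% gain is 0.05 × 18 = 0.9 kg at the minimum weight at consent (Protocol 5.1.1), and 0.05 × 35 = 1.75 kg at 35 kg, a weight-band limit used in LIN-MD-62 and LIN-MD-63 only.

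**The dash.** In Table B-1 a dash means that no limit applies, so the natural reading of the weight row is that change alone decides. Read literally, footnote a needs an observed-value criterion that weight lacks, and then not even a 5% loss could be flagged. The text should say which is meant.

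**The case against.** The strongest reply on weight is that PCS tables are screening displays in a study with no hypothesis and no inferential test, and that weight is reported in other ways. SAP 9.4 gives weight change at each visit. On subgroups, SAP 9.1 says: "All safety analyses or summaries will be performed by study intervention group using the safety population, for overall and for each age group", with FC and IBS-C kept apart. High and Low are separate flags. All of this stands. It rules out two inferences a reader might draw: that weight cannot be interpreted under this plan, and that growth hides weight loss in the flag counts. It does not cure the High flag itself, because splitting by age group changes the display and not the threshold, and does not separate entry routes.

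A reader might also infer that most children will be flagged. The documents do not support that, since without growth rates the result runs from no route to nearly all.

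On height, the reply is that this is a drafting slip. The protocol requirement still holds, and SAP 1.0 places table specifications in a separate document, not available here, which may include height. That is fair, and nothing supports inferring that the sponsor chose to drop height. The SAP text still does not carry out the protocol on this point.

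**Conclusion.** Both parts hold, and both should be corrected before database lock. The height omission is a direct mismatch between Protocol 9.4.3 and SAP 9.4 and rests on no assumption, apart from the unseen table specifications. The weight criterion can label ordinary growth as potentially clinically significant. The trigger ranges from about 11% per year (FC late entrants) to about 4% per year (LIN-MD-64 IBS-C rollovers), given a lead-in baseline at the start of lead-in treatment and steady growth. How far growth fills the PCS High table, the listing and the adverse event display cannot be determined from the documents. The consequence is confined to how descriptive safety outputs read.

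**What to change.** 1. Add height, and its change from baseline to EOT, to SAP 9.4, taking rollover baselines from lead-in data.
2. In Table B-2, remove the raw 5% High flag for weight from the PCS outputs and keep the 5% Low flag. State in the SAP that weight is judged on change only, as an exception to footnote a and to the both-criteria sentences in SAP 9.4 and Protocol 9.4.3.
3. Optional: add descriptive change in age- and sex-standardised z-scores, for weight at each weight visit and for height at EOT. Use one growth reference named before database lock. It should extend past 18, because an IBS-C participant enrolled at 18 can be 19 at EOT.

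Items 1 and 2 are the minimum: a few lines of SAP text, small programming changes and no new measurements in LIN-MD-66. The small downside of item 2 is that large gains are then seen only in the weight-change-by-visit summary. Item 3 needs the choice of a reference and some further programming.
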